5.5. Inclusion criteria

- Age ≥ 10 years and ≤ 50 years
- Absence of symptomatic falciparum malaria, defined by fever on enrolment
- Presence of *P. falciparum* gametocytes on thick blood film at a density >16 gametocytes/ μL (i.e. \geq gametocytes recorded in the thick film against 500 white blood cells)
- Absence of other non-*P. falciparum* species on blood film
- Haemoglobin ≥ 10 g/dL
- Individuals weighing $<= 80$ kg
- No evidence of acute severe or chronic disease
- Written, informed consent

5.6. Exclusion criteria

- Women who are pregnant or lactating (tested at baseline). Urine and/or serum pregnancy testing (β -hCG) will be used.
- Detection of a non-*P. falciparum* species by microscopy
- Previous reaction to study drugs / known allergy to study drugs, such as sudden high fevers, shaking or severe sore throat or ulcers in the mouth during treatment with Amodiaquine
- Current eye disease with retinal damage
- Signs of severe malaria, including hyperparasitaemia (defined as asexual parasitaemia $> 100,000$ parasites / μL)
- Signs of acute or chronic illness, including hepatitis
- The use of other medication (except for paracetamol and/or aspirin), including antacids, other medicines used to treat malaria, abnormal heart rhythm, depression or mental illness or HIV/AIDS, and medicines that have antibiotic/antifungal properties
- Use of antimalarial drugs over the past 7 days (as reported by the participant)
- Clinically significant illness (intercurrent illness e.g., pneumonia, pre-existing condition e.g., renal disease or HIV/AIDS, malignancy or conditions that may affect absorption of study medication e.g., severe diarrhoea or any signs of malnutrition as defined clinically)
- Signs of hepatic injury (such as nausea and/or abdominal pain associated with jaundice) or known severe liver disease (i.e., decompensated cirrhosis, Child Pugh stage B or C)
- Signs, symptoms or known renal impairment
- Clinically significant abnormal laboratory values as determined by history, physical examination, or routine blood chemistries and haematology values (laboratory guideline values for exclusion are haemoglobin < 10 g/dL, platelets $< 50,000/\mu\text{L}$, White Blood Cell count (WBC) $< 2000/\mu\text{L}$, serum creatinine $> 2.0\text{mg/dL}$, or ALT more than 3 times the upper limit of normal for age).
- Blood transfusion in the last 90 days.
- Known Electrocardiogram (ECG) corrected QT interval of more than 450 ms
- Documented or self-reported history of cardiac conduction problems
- Documented or self-reported history of epileptic seizures

6. STUDY DRUGS

6.1. Artesunate-Amodiaquine (ASAQ)

Participants in the ASAQ arm will receive a fixed-dose combination in tablets containing 50mg/135 mg or 100mg/270 mg of artesunate/amodiaquine (Fosun Pharma, Shanghai, China). Tablets will be administered according to manufacturer guidelines (**Table 2**).

Table 2. ASAQ dosing

Weight	Tablets	D0	D1	D2
9 to < 18 kg	50 mg AS/135 mg AQ base	1 tab	1 tab	1 tab
18 to < 36 kg	100 mg AS/270 mg AQ base blister pack of 3 tab	1 tab	1 tab	1 tab
≥ 36 kg	100 mg AS/270 mg AQ base	2 tab	2 tab	2 tab

	blister pack of 6 tab		
--	-----------------------	--	--

6.2. Primaquine (PQ)

Participants in the ASAQ-PQ arm will receive PQ (ACE Pharmaceuticals, Zeewolde, The Netherlands) at a single low dose of 0.25mg/kg as is currently recommended by the World Health Organization. The single dose of PQ will be given on day 0 together with ASAQ, administered in an aqueous solution, according to a standard operating procedure (SOP) provided by the manufacturer as previously done at the study site when PQ was combined with DP, PA, AL [3], [8], [23].

6.3. Artemether-Lumefantrine (AL)

Participants in the AL arm will be treated with standard doses of AL (Fosun Pharma, Shanghai, China). Tablets containing 20 mg artemether and 120 mg lumefantrine will be administered per manufacturer guidelines (**Table 3**)

Table 3. AL dosing

Bodyweight (kg)	20/120 mg tablet		
	D0	D1	D2
5 to < 15 kg	1 disp tab x 2	1 disp tab x 2	1 disp tab x 2
15 to < 25 kg	2 disp tab x 2	2 disp tab x 2	2 disp tab x 2
25 to < 35 kg	3 tab x 2	3 tab x 2	3 tab x 2
≥ 35 kg	4 tab x 2	4 tab x 2	4 tab x 2

6.4. Amodiaquine (AQ)

Participants in the ALAQ and ALAQ-PQ arms will receive AQ as tablets of 153 mg. The weight-based treatment schedule in **table 4** aims for a dosage of approximately 10 mg (7.7-15.3mg)/kg/day, given once or twice daily (together with artemether-lumefantrine) for three days.

Table 4. AQ dosing

Bodyweight (kg)	153 mg tablet					
	D0 (0hr)	D0 (8hr)	D1 (24hr)	D1 (36hr)	D2 (48hr)	D2 (60hr)
10 to 19.9	1 tab	0 tab	1 tab	0 tab	1 tab	0 tab
20 to 29.9	1 tab	1 tab	1 tab	1 tab	1 tab	1 tab
30 to 54.9	2 tab	1 tab	2 tab	1 tab	2 tab	1 tab
55 to 80	3 tab	2 tab	3 tab	2 tab	3 tab	2 tab

7. OUTCOME MEASURES

7.1. Primary outcome measure

Median within person percent change (presented as percent reduction) in mosquito infection rate in infectious individuals from baseline (day 0, pre-treatment) to day 2 post treatment in the ASAQ, ASAQ-PQ, AL, ALAQ and ALAQ-PQ arms.

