5.4. Sample size calculation

For sample size considerations, we estimated the infectivity for participants in previous trials in the same study setting [3], [4], [8], [23] using a mixed effects logistic regression model that accounted for correlation between mosquito observations from the same participant. Based on a mixed effects logistic regression we looked at 100 simulations with an expected reduction in infectivity of 90%, an expected baseline proportion of infectivity of 17% for the average participant, and an expected intra-cluster correlation of 0.5. We estimated 88% empirical power to detect $>80\%$ reduction in infectivity with a one-tailed test with a 0.025 level of significance when including 20 participants and dissecting 50 mosquitos per participant at each timepoint.

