11.1. Analysis plan

Mosquito infectivity will be assessed at three levels: the mean number of oocysts in a sample of mosquitoes (i.e. oocyst intensity), the proportion of mosquitoes infected with any number of oocysts (i.e. mosquito infection rate), and the infectivity of the study participant to any number of mosquitoes (i.e. infectivity to mosquitoes). The primary outcome measure will be the percent change in mosquito infection rate within each arm by day 2 compared to baseline, with other time-points of infectivity assessments as secondary outcomes. Percent change will be reported as percent reduction (with 100% as total reduction of transmission, and negative values as enhanced transmission). Other secondary transmission outcomes are as described in the 'Objectives' section above. Some exploratory objectives may be published separately from the main primary/secondary outcomes.

Statistical analysis will be conducted using the most recent STATA and SAS versions (16.0 and SAS version 9.4 at time of writing). Mosquito infection data will be analysed at time-points after baseline only for those individuals who are infectious at baseline, although the data and analyses from all enrolled individuals will be published in the appendix for completeness. Individuals will be classified as infectious to mosquitoes if they infect at least 1 mosquito, with any number of oocysts. Infectivity to mosquitoes and parasite/gametocyte prevalence will be compared within and between treatment arms using generalised linear models (family: binomial, z-score, co-efficient with 95% CI) or fishers exact tests. Absolute haemoglobin density and percent change in haemoglobin density (relative to baseline) will be compared using paired t-tests (t-score for difference compared to day 0) and two-way t-tests (t-score for difference between ACT matched treatment groups at each time-point). The proportion of gametocytes that are male will be calculated for all values with total gametocyte densities of 0.2/ μ L and over. Gametocyte circulation time will be calculated to determine the average period (in days) that a mature gametocyte circulates in the blood prior to clearance, using a deterministic compartmental model that assumes a constant rate of clearance and has a

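### The primary summary, a median of within-person percent reductions, reads exactly 100% once more than half of the participants fall to zero, so it needs an arm-level reduction with a confidence interval beside it

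*Protocol*

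**What the plan says.** Section 7.1 sets the primary outcome as "Median within person percent change (presented as percent reduction) in mosquito infection rate in infectious individuals from baseline" to day 2, in each of the five arms. Section 11.1 restricts the analysis set: "Mosquito infection data will be analysed at time-points after baseline only for those individuals who are infectious at baseline". It also fixes the scale: "Percent change will be reported as percent reduction (with 100% as total reduction of transmission, and negative values as enhanced transmission".

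Section 5.4 sizes the trial on a different quantity. It uses a mixed effects logistic regression and "100 simulations with an expected reduction in infectivity of 90" per cent, with "an expected baseline proportion of infectivity of 17% for the average participant" and "an expected intra-cluster correlation of 0.5". The test is against a reduction of 80%, one-tailed at 0.025, with 20 participants and 50 dissected mosquitoes per participant and time-point. The stated empirical power is 88%.

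In section 7.2 both secondary outcomes on the mosquito infection rate are again medians. The other two infectivity outcomes are whether a participant infects any mosquito, and mean oocyst intensity.

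**The concern.** A median gives every participant the same weight and ignores how far the less favourable half lies from the middle. Participants who infect few mosquitoes at baseline easily drop to 0 of about 50 and then score 100%. Highly infectious participants supply most of the infected mosquitoes and are the likeliest to keep infecting some. Once more than half score 100%, the summary stops responding to what the rest transmit.

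The primary figure could then be 100% in an arm that still infects mosquitoes. A reader who carries the section 11.1 meaning of 100% over to the arm would take that as complete blocking. The figure also differs in kind from the modelled reduction that section 5.4 tests against 80%, so the sample size does not speak directly to the number reported as primary.

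**Working it through.** **1. The ceiling is arithmetic.** Take 20 participants with 9/50 infected mosquitoes each at baseline. On day 2, 11 have 0/50 and 9 have 3/50.
- Within-person reductions: eleven at 100%, nine at 1 − 3/9 = 67%. The 10th and 11th ranked values are both 100%, so the median is 100%.
- Infected mosquitoes: 20 × 9 = 180 before, 9 × 3 = 27 after. Remaining: 27/180 = 15%.

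**2. Inputs for the simulation.** From section 5.4: baseline 17% for the average participant, intra-cluster correlation (ICC) 0.5, 20 participants, 50 mosquitoes. From sections 7.1 and 11.1: baseline-infectious participants only. Assumption: the ICC is on the latent logit scale, which section 5.4 does not state. Then 0.5 = σ²/(σ² + π²/3), so σ = √(π²/3) = 1.81. About 18 of 20 participants are infectious at baseline.

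**3. The plan's own figure.** Power was re-simulated with a random-intercept logistic model and a one-sided Wald test against 80%. Most readings give 93-97%. Simulating the effect on odds and testing the probability ratio gives 84%. The stated 88% lies between these, and 100 simulations carry a margin of about 1.96 × √(0.88 × 0.12/100) = 6 points. The figure is neither reproduced exactly nor shown to be wrong, and nothing below depends on it.

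**4. How often the median is 100%, and what remains.** There were 40,000 simulated arms per row. With participant effect u ~ N(0, σ²), p0 = expit(logit(0.17) + u). The reduction r was applied in two main ways:
- common logit shift: p2 = expit(logit(0.17 × (1 − r)) + u)
- same proportional cut in everyone: p2 = p0 × (1 − r)

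Median = median of 1 − x2/x0 over participants with x0 > 0. Residual = Σx2/Σx0 over the same participants.

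| True reduction r | Arms with median exactly 100% (logit shift / proportional) | Mean residual (logit shift / proportional) |
|---|---|---|
| 90% | 13% / 16% | 21% / 10% |
| 95% | 53% / 69% | 12% / 5% |
| 97% | 82% / 94% | 8% / 3% |

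Reading r as a fall in odds gives 8%, 41% and 73% of arms, with residuals of 23%, 14% and 9%.

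Among arms at r = 95% whose median is 100%, 37-39% of baseline-infectious participants still infect at least one mosquito. The 5th, 50th and 95th percentiles of the residual in those arms are 4.9, 9.8 and 19.8% (logit shift) and about 2.6, 4.5 and 6.8% (proportional).

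**5. The design value.** At r = 90% the typical arm median is 90% (logit shift) or 93% (proportional). The pooled fall is 100 − 21 = 79% or 100 − 10 = 90%. Under the logit shift the two measures answer different questions: the reduction for an average participant, and the reduction in all infected mosquitoes.

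**The case against.** - **The 100% wording.** A reader might infer that the protocol itself treats an arm median of 100% as total blocking. It does not. "Percent change will be reported as percent reduction (with 100% as total reduction of transmission" anchors the percent-change scale and is correct for one person's assay. The difficulty arises only if that meaning is carried to the arm median. This part of the objection stands.
- **Matched arms.** A reader might infer that the measure cannot separate two strong arms. Between-arm comparisons are secondary and, for quantitative data, use Wilcoxon rank-sum tests on every participant's value. In simulations of 95% against 99%, such a test had 51-59% power, and it still separated the arms in 25-43% of trials where both medians were 100%. The ceiling limits the displayed effect size, not the test.
- **90% against 79%.** A reader might call this gap an error. It is a difference of estimand. The primary objective in section 4.1 asks for a within-person reduction, and section 5.4 is framed on the average participant. A median is a fair description of the typical participant.
- **Replacing the primary outcome.** Under the logit-shift reading, a population-averaged reduction averages 79% at the design value (5th to 95th percentile 69-88%), below the 80% benchmark. Substituting it would undo the stated power, so it is more than a change of wording. That argues for adding the figure, not for replacing the median.
- **Other outcomes show the residual.** Partly true. The outcome on infecting any mosquito would show that over a third of participants still transmit, and section 11.1 promises appendix data on everyone enrolled. Neither gives the arm-level fall in mosquito infection rate.
- **High efficacy is assumed.** Section 3.1 reports effective blockage within 48 hours when primaquine was added to other combinations, without a percentage. The 95% and 97% scenarios are assumptions.

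**Conclusion.** The point holds in a limited form. The primary median saturates at exactly 100% once more than half of the baseline-infectious participants reach zero. At the planned 90% reduction this is uncommon (about 13-16% of arms). At 95% it happens in 53-69% of arms with 5-12% of infected mosquitoes remaining on average, and at 97% in 82-94% with 3-8% remaining.

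The residuals are simulated, not taken from the protocol. They rest on the section 5.4 inputs, the logit scale for the ICC, and two ways of applying the reduction; the odds reading gives fewer saturated arms and larger residuals. The primary outcome is not invalid, and the residual is not hidden from the secondary analyses. What is missing is an arm-level effect size of the kind the sample size rests on, and a statement of what an arm median of 100% means. This is a worthwhile, low-cost improvement.

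**What to change.** In sections 7.1 and 11.1:

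1. Keep the median, with its IQR.
2. Beside it, report for each arm the day 2 versus day 0 relative reduction in mosquito infection rate from the mixed-effects logistic model of section 5.4, with a participant-clustered 95% confidence interval.
3. State whether that reduction is for the average participant (the scale of the 80% and 90% figures in section 5.4) or population-averaged. Only the former can be set directly against the 80% benchmark.
4. State that an arm median of 100% means that more than half of the baseline-infectious participants fell to zero, not that transmission from the arm was fully blocked.

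Cost: a little more analysis and no extra participants, visits or samples. The model-based figure will often look less favourable than the median.

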7.2. Secondary outcome measures

- Median within person percent change (presented as percent reduction) in mosquito infection rate from baseline to all feeding time-points, with comparison within and between arms.
- Median mosquito infection rate at all feeding time-points, with comparison within treatment arms compared to baseline, and between arms.
- Infectivity to mosquitoes at all feeding time-points, with comparison within treatment arms compared to baseline, and between arms.
- Mean oocyst intensity (in all/all infected mosquitoes) at all feeding time-points, with comparison within treatment arms compared to baseline, and between arms.
- Male and female gametocyte prevalence at all time-points, determined by microscopy or molecular assays, with comparison within treatment arms compared to baseline, and between arms.
- Male and female gametocyte density at all time-points, determined by microscopy or molecular assays, with comparison within treatment arms compared to baseline, and between arms.
- Male and female gametocyte sex ratio (proportion male) at all time-points, determined by microscopy or molecular assays, with comparison within treatment arms compared to baseline, and between arms.
- Gametocyte circulation time (cumulative), determined by microscopy or molecular assays, compared between treatment arms.
- Gametocyte area under the curve (cumulative), determined by microscopy or molecular assays, compared between treatment arms.
- Asexual and total parasite prevalence at all time-points, determined by microscopy or molecular assays, with comparison within treatment arms compared to baseline, and between arms.
- Asexual and total parasite density at all time-points, determined by microscopy or molecular assays, with comparison within treatment arms compared to baseline, and between arms.
- Haemoglobin density at all time-points, with comparison within treatment arms compared to baseline, and between arms.
- Median within person percent change (presented as percent reduction) in haemoglobin density from baseline to all time-points, with comparison within and between arms.
- The frequency and prevalence of adverse events (all AE's, treatment related AE's, and haematological AE's) observed up to and including day 2, 7, and 14 post-treatment, and at all timepoints.

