4.2. Secondary specific objectives

- To assess differences in other mosquito infectivity parameters (mosquito infection rate, change in infection rate, infectivity to mosquitoes, and oocyst density) following treatment with ASAQ, ASAQ-PQ, AL, ALAQ and ALAQ-PQ in children and adults at all feeding timepoints compared to pre-treatment (day 0) and between treatment matched arms (ASAQ vs ASAQ-PQ, AL vs ALAQ, ALAQ vs ALAQ-PQ).
- To assess differences in gametocyte parameters (prevalence, density, circulation time, area-under-the-curve, sex-ratio) following treatment with ASAQ, ASAQ-PQ, AL, ALAQ and ALAQ-PQ in children and adults at all feeding timepoints compared to pre-treatment (day 0) and between treatment matched arms (ASAQ vs ASAQ-PQ, AL vs ALAQ, ALAQ vs ALAQ-PQ).
- To assess differences in safety parameters (AE frequency, Hb density, median drop in Hb) following treatment with ASAQ, ASAQ-PQ, AL, ALAQ and ALAQ-PQ in children and adults at all feeding timepoints compared to pre-treatment (day 0) and between treatment matched arms (ASAQ vs ASAQ-PQ, AL vs ALAQ, ALAQ vs ALAQ-PQ).
- To assess differences in biochemical parameters (ALT, CBC, Creatinine) following treatment with ASAQ, ASAQ-PQ, AL, ALAQ and ALAQ-PQ in children and adults at all feeding timepoints compared to pre-treatment (day 0) and between treatment matched arms (ASAQ vs ASAQ-PQ, AL vs ALAQ, ALAQ vs ALAQ-PQ).

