random effect to account for repeated measures on individuals, as described previously [29]; circulation time will be analysed using t-tests (t score for difference between ACT matched treatment groups) or linear regression analyses. Area under the curve (AUC) of gametocyte density per participant over time will be calculated using the linear trapezoid method [30] using the first 28 days of observation only, and analysed by fitting linear regression models to the log10 adjusted AUC values, with and without adjustment for baseline gametocyte density (t-score, coefficient with 95% CI). All other analyses of quantitative data will be performed using Wilcoxon sign rank tests (z-score for difference compared to matched values at day 0) and Wilcoxon rank-sum tests (z-score for difference between ACT matched treatment arms at each time-point). The nonparametric van Elteren's test, an extension of the Wilcoxon rank sum test, will be used to compare the infectivity between treatment arms after adjusting for gametocyte density, as previously described [19]. This will compare infectivity between groups after stratifying into categories based on total gametocytes per microliter. Within these bins differences in infectivity between arms will be tested, thereby investigating sterilizing effects of gametocytocidal drugs. For all analyses, the threshold for statistical significance will be set at $p < 0.05$.

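### The infected-mosquitoes-only version of oocyst intensity has no value for a participant who infects no mosquito, so its planned tests run on a subset selected by treatment (minor)

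*Protocol*

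**What the plan says.** Section 7.2 of the protocol names the outcome in two versions and asks for both kinds of comparison: "Mean oocyst intensity (in all/all infected mosquitoes) at all feeding time-points, with comparison within treatment arms compared to baseline, and between arms". Section 4.2 lists the infectivity parameters as "mosquito infection rate, change in infection rate, infectivity to mosquitoes, and oocyst density". Section 11.1 describes the measure as "the mean number of oocysts in a sample of mosquitoes (i.e. oocyst intensity".

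Section 11.1 gives oocyst intensity no test of its own, so it falls under the general rule there. For change from baseline within an arm, that rule reads "All other analyses of quantitative data will be performed using Wilcoxon sign rank tests (z-score for difference compared to matched values at day 0". The same rule then turns to comparisons across arms, for which it names a different procedure: "Wilcoxon rank-sum tests (z-score for difference between ACT matched treatment arms at each time-point".

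Two further statements in section 11.1 fix who is analysed. One restricts the post-treatment data: "Mosquito infection data will be analysed at time-points after baseline only for those individuals who are infectious at baseline". The other sets what counts as being infectious: "Individuals will be classified as infectious to mosquitoes if they infect at least 1 mosquito, with any number of oocysts".

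The protocol gives no infected-only value to a participant who infects no mosquito after treatment, and it does not mark the infected-only comparison as descriptive.

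**The concern.** Everyone analysed after baseline has infected at least one mosquito at day 0, so the infected-only mean always exists at day 0. Afterwards it exists only for participants who still infect at least one mosquito. Having a value therefore depends on the effect the drugs are meant to produce, and the more effective arm loses more participants. A between-arm test on those who remain is no longer a comparison of the groups as randomised, and the paired test within an arm leaves out participants with no detected transmission.

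The comparisons most exposed are ASAQ against ASAQ-PQ and ALAQ against ALAQ-PQ, where added primaquine is expected to stop most transmission. A non-significant infected-only result from a few residual transmitters could be read as no effect on oocyst burden. Every participant is fed on at days 2, 7 and 14, so the loss comes from the definition of the measure and not from the conditional feeds at days 21 and 28.

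**Working it through.** **The plan's own figure.** Section 5.4 states 88% power, but for the primary outcome; nothing is stated for oocyst intensity. Re-simulating section 5.4 gave 84% to 99%, depending on how the reduction and the null are scaled. With only 100 simulations, the stated 88% has a 95% interval of about 80–94%. It is not shown to be wrong, and nothing below depends on it.

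**The two versions on illustrative records (3 oocysts per infected mosquito).**

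| Feed | All mosquitoes | Infected only |
|---|---|---|
| Day 0, 10/50 infected | 30/50 = 0.60 | 30/10 = 3.0 |
| Day 2, 1/50 infected | 3/50 = 0.06 | 3/1 = 3.0 |
| Day 2, 0/50 infected | 0/50 = 0 | 0/0, no value |

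The second row is not an error: the two versions answer different questions. The third row is the problem.

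**How many participants have no value at day 2.** Inputs from section 5.4: baseline 17% for the average participant, intra-cluster correlation 0.5, 50 mosquitoes, 20 participants per arm, and "an expected reduction in infectivity of 90"%. Assumption: the correlation is on the logit scale, so σ²/(σ² + π²/3) = 0.5 and σ = π/√3 = 1.81.

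- Baseline infection probability: p0 = expit(logit 0.17 + u), with u ~ N(0, σ²).
- Infectious at baseline: E[1 − (1 − p0)^50] = 0.909, and 20 × 0.909 = 18.2 per arm.
- No value at day 2, given infectious at baseline: E[{1 − (1 − p0)^50}(1 − p2)^50] / 0.909.

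The protocol does not say on which scale the reduction r acts. Three choices for p2 were used: p0 multiplied by (1 − r); the odds multiplied by (1 − r); and the average participant's probability set to 0.17(1 − r) with the same u.

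| Reduction | No infected-only value | Left of 18.2 |
|---|---|---|
| None | 5% | 17.3 |
| 50% | 11–12% | 16.1–16.3 |
| 90% | 35–40% | 10.9–11.8 |
| 99% | 77–87% | 2.3–4.2 |

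With σ = 1.0 instead, the loss is 37–42% at a 90% reduction and 86–90% at 99%.

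**Paired test.** With n untied pairs, the smallest exact two-sided signed-rank p-value is 2/2^n: 0.0625 for n = 5 and 0.031 for n = 6. At a 99% reduction (third scale), 82–85% of simulated arms had fewer than 6 usable participants and so could not reach p < 0.05.

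**Between-arm test.** The protocol gives no oocyst distribution, so negative-binomial counts were assumed (k from 0.3 to 3 across the runs). For a 50% against a 90% reduction, rank-sum power was about 47–72% with all mosquitoes and about 14–32% with infected mosquitoes only. These levels move with the assumptions. A further check with the reduction applied to the infection probability gave about 91–94% against 52–70%. The infected-only test was the weaker in every setting; the size of the gap is only illustrative.

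**The case against.** The strongest reply is that the protocol already contains what is needed. The all-mosquito version stands in the same line of section 7.2. Infection rate, its percent change and infectivity to mosquitoes all keep a 0/50 feed as a zero or a 100% reduction. This stands, and it limits the point to one version of one secondary outcome.

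A second reply is that infected-only intensity is a legitimate measure of burden once a mosquito is infected, in a trial with a stated interest in how the drugs act. That also stands as a reason to keep reporting it. It does not make a test among residual transmitters a randomised comparison.

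A third reply is that the protocol nowhere says these participants are dropped, that the rank tests come from a general rule, and that the handling of missing values may be left to the SAP. The wording is indeed indirect. But section 7.2 itself asks for both comparisons of this version, and a 0/0 record cannot enter either test unless some value is assigned to it.

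Two stronger readings are tempting and are not supported. A reader might infer that section 11.1 contradicts section 7.2. It does not: a mean over a sample of mosquitoes neither includes nor excludes an infected-only version, and the change between density and intensity is a matter of naming with no shown consequence. A reader might also infer that a highly effective arm would tend to look no better, or worse, than its comparator. One can build such a case by letting primaquine block most participants completely and leave the rest responding like controls. Burden among those still infectious is then equal in both arms, and failing to reject is the correct answer to the infected-only question. In the 50% against 90% simulations the direction was kept: with k = 0.5 the infected-only median averaged 1.27 in the weaker arm and 1.03 in the stronger.

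**Conclusion.** The point holds in a limited form. Followed as written, the plan tests infected-only oocyst intensity on a subset selected by the treatment's own effect. At the planned 90% reduction about 35–40% of baseline-infectious participants have no value at day 2, and at 99% it is 77–87%, against about 5% with no effect. These shares rest on the section 5.4 inputs, the logit-scale reading of the correlation, and the scale of the reduction, which is why they are ranges. Some zero feeds occur by chance, as the 5% shows, so a missing value means no detected transmission and not proof of cure.

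The consequences are reduced sensitivity and a comparison that is not randomised; a systematic reversal of direction is not shown. The power figures also need the assumed oocyst distribution and serve as illustration only. The primary outcome, the all-mosquito mean and the other infectivity outcomes are unaffected. Severity is minor.

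**What to change.** In sections 7.2 and 11.1, make mean oocysts per dissected mosquito the version used for the within-arm and between-arm tests, with uninfected mosquitoes kept as zeros and a feed with no infected mosquito counted as 0. Report the mean in infected mosquitoes descriptively, labelled as conditional on infection, with the number of contributing participants per arm and visit, and state that it is not to be interpreted as a randomised treatment comparison. Using one term for the measure in sections 4.2, 7.2 and 11.1 would be tidy.

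The change is wording only and uses the same dissection data. The cost is losing a p-value for the infected-only version.
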